## **1. INTRODUCTION**

This statistical analysis plan provides a technical and detailed elaboration of the statistical analyses of pharmacokinetic (PK), safety, and tolerability data as described in the final study protocol SHP465-112 version 1.0 dated 15 Sep 2017 and the protocol administrative change #1 dated 31 Oct 2017. Specifications for tables, figures, and listings are contained in a separate document.

## 2. STUDY DESIGN

### 2.1 General Study Design

The study will be a Phase 1, open-label, multiple-dose, PK, safety, and tolerability study in children aged 4 to 5 years diagnosed with attention-deficit/ hyperactivity disorder (ADHD). Enrollment will be stratified by sex to ensure that at least 2 of the 10 subjects expected to complete the rich PK sampling portion of the study and at least 3 of the 10 subjects expected to complete the sparse PK sampling portion of the study are females.

Following the screening visit, eligible subjects will return to the clinical research center (CRC) on Day 1 of Week 1 to reconfirm eligibility criteria and enter into the treatment phase. Total duration for the treatment period is approximately 30 days for subjects in the rich PK sampling portion of the study and 29 days for subjects in the sparse PK sampling portion of the study. In the study, single 6.25 mg dose of SHP465 will be administered daily for 28 days ( $\pm 1$  day) at 8:00 AM ( $\pm 1$  hour).

#### Rich PK Sample Scheme (9 Samples/Subject) Collection

Predose PK samples will be collected on Day 1 of Week 1, and serial blood samples for PK analysis will be drawn prior to dosing on Day 7 of Week 4 (within 60 minutes prior to dosing) and up to 48 hours after administration of the investigational product (IP).

On Day 7 of Week 4, subset of subjects in the rich PK sampling portion will be required to remain at the CRC through 8 hours postdose. Following completion of the 8-hour PK sample collection, per investigator's discretion, subjects will have the option to remain at or leave the CRC. If they leave the CRC, subjects will either return to the CRC on Days 7, 8, and 9 of Week 4 for the 12-hour, 16-hour, 24-hour, and 48-hour postdose blood sample collections or, if the option is available at their clinical site, a qualified person may visit the subject for the 12-hour, 16-hour, and 24-hour postdose blood sample collections, but they must return to the clinic for the 48-hour blood sample collection.

#### Sparse PK Sample Scheme (4 Samples/Subject) Collection

Predose PK samples will be collected on Day 1 of Weeks 1 to 3 and on Day 8 of Week 4 (24 hours after dosing on Day 7 of Week 4) for subjects in the sparse PK sampling subset.

### 2.2 Randomization

Not applicable.

### 2.3 Blinding

This is an open-label study so blinding is not applicable.

## 2.4 Schedule of Assessments

**Table 1: Schedule of Assessments for Rich Pharmacokinetic Sampling Portion**

Assessment Day	Screening and Washout		Week 1 to 3		Week 4								Follow-up a		
	D -32 to D -8	D -7 to D -1 Washout	D 1	D 2-7	D 1	D 2-6	D 7								
Treatment Week 4 Time point (h)							Predosec	0	2	5	8	12	16	24	48
Informed Consent & Assent	X														
Inclusion/Exclusion Criteria	X		X d												
Demographics	X														
Medical & Medication History (Includes Prior Medications and Procedures) e	X														
Physical Examination	X		X f		X f		X g							X h	
Vital Signs i	X		X		X		X			X				X h	
Weight j	X		X		X		X							X h	
Height j	X													X h	
Biochemistry, Hematology, and Urinalysis	X													X h	
TSH, T4, and T3	X													X h	
Urine Drug and Alcohol Screen	X														
12-lead ECG i	X		X				X			X				X h	
C-SSRS Baseline Version	X														
C-SSRS Since Last Visit Version			X		X		X							X h	
MINI-KID	X														
ADHD-RS-5 Child, Home Version	X														
Clinical Global Impressions – Severity of Illness	X														
CSHQ	X		X		X		X							X h	
PSQ	X		X		X		X							X h	
Eligibility Confirmation			X d												
Investigational Product Dispensed			X		X										
Investigational Product Administration			X k	X l	X k	X l		X k,m							
Pharmacokinetic Sample Collection			X n				X		X	X	X	X	X	X	
Concomitant Medications	X	X	X	X	X	X	X	X	X	X	X	X	X	X h	X

**Table 1: Schedule of Assessments for Rich Pharmacokinetic Sampling Portion**

Assessment Day	Screening and Washout		Week 1 to 3		Week 4						Follow-up a			
	D -32 to D -8	D -7 to D -1 Washout	D 1	D 2-7	D 1	D 2-6	D 7				D 8 b	D 9 /ET b		
Adverse Events	X	X	X	X	X	X	X	X	X	X	X	X	X h	X

ADHD-RS-5=Attention-Deficit/Hyperactivity Disorder Rating Scale-5; CRC=clinical research center; C-SSRS=Columbia-Suicide Severity Rating Scale; CSHQ=Children's Sleep Habits Questionnaire; D=day; ECG=electrocardiogram; ET=Early Termination; h=hours; MINI-KID=Mini International Neuropsychiatric Interview for Children and Adolescents; PSQ=Post Sleep Questionnaire; TSH=thyroid-stimulating hormone; T3=tri-iodothyronine; T4=thyroxine.

a Follow-up contact will be conducted approximately 1 week (7 days [ $\pm 2$  days]) following the last dose of investigational product.

b Day 8 and Day 9 may be conducted on an out-patient basis.

c These assessments should be performed within 2 hours prior to dose administration with the exception of the pharmacokinetic sample, which should be collected within 60 minutes prior to dosing.

d Inclusion/exclusion criteria and eligibility confirmation must be reviewed at the CRC on Day 1 of Week 1.

e Medical and medication history will include a detailed description of the subject's psychiatric diagnosis and a lifetime history of pharmacologic therapies for ADHD and other disorders.

f A brief physical examination will be performed prior to dosing on Day 1.

g A brief physical examination will be performed prior to dosing on Day 7 of Week 4.

h An attempt to perform these assessments and procedures will be made for any subjects who withdraw or are removed from the study.

i Subjects should be resting in a sitting position for at least 5 minutes prior to collecting vital signs (systolic and diastolic blood pressure, pulse rate, respiratory rate, and body temperature). Subjects should be resting in a supine position for at least 5 minutes prior to collecting ECGs. If an invasive procedure was conducted prior to blood pressure, ECG and respiratory rate recording, the subject should be resting for 15 minutes.

Blood pressure and pulse will be measured at each visit. Measurements of blood pressure and pulse will be performed 3 times (with at least 2 minutes in between each collection) using the provided age-appropriate cuff. The average of each set of 3 measurements will be used to determine continued participation in the study.

Temperature and respiratory rate will be collected at the screening visit and ET visit only.

Measurement of blood pressure and pulse will be performed 3 times (with at least 2 minutes in between each collection) using the provided age-appropriate cuff.

j Height and weight to be measured without shoes and with light clothing using a stadiometer for height and calibrated scale for weight.

k Dosing will be done at the CRC.

l Dosing will be done at the home.

m Subjects should fast for 2 hours prior to dose administration on Day 7 of Week 4 and for 2 hours postdose. At 2 hours postdose on Day 7, subjects will be allowed to consume a light breakfast, ie, a single serving of cereal with up to 8 ounces of skim milk. Starting at 4 hours postdose on Day 1, for lunch and dinner, subjects will receive a standardized moderate fat meal. Subjects will be allowed snacks starting after lunch.

n To be sampled predose on Week 1 only.

Whenever possible, the same individual should complete/rate consistently the following scales and questionnaires as appropriate: ADHD-RS-5 Child, Home Version; Clinical Global Impressions - Severity of Illness; Post Sleep Questionnaire; and Children's Sleep Habits Questionnaire.

**Table 2: Schedule of Assessments for Sparse Pharmacokinetic Sampling Portion**

**Table 2: Schedule of Assessments for Sparse Pharmacokinetic Sampling Portion**

Assessment Day	Screening and Washout		Week 1 to 3		Week 4		Follow-upa
	D -32 to D -8	D -7 to D -1 Washout	D 1	D 2-7	D 1	D 2-7	D 8 /ET

ADHD-RS-5=Attention-Deficit/Hyperactivity Disorder Rating Scale-5; CRC=clinical research center; C-SSRS=Columbia-Suicide Severity Rating Scale; CSHQ=Children's Sleep Habits Questionnaire; D=day; ECG=electrocardiogram; ET=Early Termination; h=hours; MINI-KID=Mini International Neuropsychiatric Interview for Children and Adolescents; PSQ=Post Sleep Questionnaire; TSH=thyroid-stimulating hormone; T3=tri-iodothyronine; T4=thyroxine.

a Follow-up contact will be conducted approximately 1 week (7 days [ $\pm$ 2 days]) following the last dose of investigational product.

b Inclusion/exclusion criteria and eligibility confirmation must be reviewed at the CRC on Day 1 of Week 1.

c Medical and medication history will include a detailed description of the subject's psychiatric diagnosis and a lifetime history of pharmacologic therapies for ADHD and other disorders.

d A brief physical examination will be performed prior to dosing on Day 1 of Weeks 1 to 4.

e An attempt to perform these assessments and procedures will be made for any subjects who withdraw or are removed from the study.

f Subjects should be resting in a sitting position for at least 5 minutes prior to collecting vital signs (systolic and diastolic blood pressure, pulse rate, respiratory rate, and body temperature). Subjects should be resting in a supine position for at least 5 minutes prior to collecting ECGs. If an invasive procedure was conducted prior to blood pressure, ECG and respiratory rate recording, the subject should be resting for 15 minutes.

Blood pressure and pulse will be measured at each visit.

Temperature and respiratory rate will be collected at the screening visit and ET visit only.

g Height and weight to be measured without shoes and with light clothing using a stadiometer for height and calibrated scale for weight.

h Dosing will be done at the CRC.

i Dosing will be done at the home

## 2.5 Determination of Sample Size

To objectively justify the sample size for PK sampling and PK sampling scheme for this study, the precision below (in accordance with FDA guidance) is used.

The sample size for traditional rich PK sampling for noncompartmental analysis is calculated to achieve 80% probability (power), to ensure that the 95% confidence interval (CI) of the point estimate of the geometric mean of clearance is within 60% to 140% of the estimate of the clearance. Although the range (60-140%) is not symmetric to 1, the lower CI bound is within the minimum and maximum (60%, 140%) ( $1/1.4=0.714$ ), provided that the upper bound is  $\leq 1.4$ .

The data presented in [Table 3](#) are from Shire's completed study (SHP465-111) in pediatric subjects with ADHD and show that the reported apparent clearance (CL/F) and volume of distribution (Vz/F) for the d-amphetamine and l-amphetamine of SHP465 after oral administration of SHP465 12.5 mg in children aged 6 to 12 years and 25 mg in adolescents aged 13 to 17 years.

**Table 3: Estimates of Clearance and Volume of Distribution for *d*-Amphetamine and *l*-Amphetamine**

	SHP465 12.5 mg Children (6 to 12 years)		SHP465 25 mg Adolescents (13 to 17 years)	
CV (%)	CL/F (L/h)	Vz/F (L)	CL/F (L/h)	Vz/F (L)
d -amphetamine	25.0	28.5	23.7	18.4
l -amphetamine	26.9	32.2	28.4	22.0

CL/F=body clearance; CV=coefficient of variation; Vz/F=volume of distribution

Source: SHP465-111 Clinical Study Report (06 May 2016) Tables 9-1 and 9-4.

The sample size estimates use the within-subject *l*-amphetamine variability of 32.2%, since it is numerically bigger. Applying the methods from the manuscript by Wang et al. ([2012](#)), sample size estimations with related probability for corresponding coefficients of variation are provided as follows:

CV (%)	Number of Subjects Required	Probability of the Point Estimate Within the Prespecified Interval (%)
18.4	5	89
22.0	5	80
23.7	6	88
25.0	6	82
26.9	7	89
28.4	7	88
28.5	7	88
32.2	8	90

CV=coefficient of variation

Based on these data, the PK sampling analysis will need at least 8 subjects in total to provide reliable PK results.

Approximately 24 subjects are expected to be enrolled to ensure that 10 subjects will complete the rich PK sampling portion of the study and an additional 10 subjects will complete the sparse PK sampling portion of the study. Enrollment will be stratified by sex to ensure that at least 2 of the 10 subjects in the rich PK sampling portion of the study and at least 3 of the 10 subjects in the sparse PK sampling portion of the study expected to complete the study are females.

### **3. OBJECTIVES**

#### **3.1 Primary Objective**

To evaluate the PK, safety, and tolerability of SHP465 in children aged 4 to 5 years with ADHD after SHP465 multiple daily doses of 6.25 mg.

## **4. STUDY POPULATION SETS**

### **4.1 Screened Set**

The screened set will consist of all subjects who have provided informed consent.

### **4.2 Enrolled Set**

The enrolled set will consist of all subjects who have been assigned a subject identification number and enrolled at baseline (predose on Day 1) visit.

### **4.3 Safety Set**

The safety set will consist of all enrolled subjects who have taken at least 1 dose of investigational product.

### **4.4 Pharmacokinetic Set**

The PK set will consist of all subjects in the safety set for whom at least 1 PK blood sample was collected.

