^f A brief physical examination will be performed prior to dosing on Day 1.

^g A brief physical examination will be performed prior to dosing on Day 7 of Week 4.

^h An attempt to perform these assessments and procedures will be made for any subjects who withdraw or are removed from the study.

ⁱ Subjects should be resting in a sitting position for at least 5 minutes prior to collecting vital signs (systolic and diastolic blood pressure, pulse rate, respiratory rate, and body temperature). Subjects should be resting in a supine position for at least 5 minutes prior to collecting ECGs. If an invasive procedure was conducted prior to blood pressure, ECG and respiratory rate recording, the subject should be resting for 15 minutes.

Blood pressure and pulse will be measured at each visit. Measurements of blood pressure and pulse will be performed 3 times (with at least 2 minutes in between each collection) using the provided age-appropriate cuff. The average of each set of 3 measurements will be used to determine continued participation in the study.

Temperature and respiratory rate will be collected at the screening visit and ET visit only.

Measurement of blood pressure and pulse will be performed 3 times (with at least 2 minutes in between each collection) using the provided age-appropriate cuff.

^j Height and weight to be measured without shoes and with light clothing using a stadiometer for height and calibrated scale for weight.

^k Dosing will be done at the CRC.

^l Dosing will be done at the home.

^m Subjects should fast for 2 hours prior to dose administration on Day 7 of Week 4 and for 2 hours postdose. At 2 hours postdose on Day 7, subjects will be allowed to consume a light breakfast, ie, a single serving of cereal with up to 8 ounces of skim milk. Starting at 4 hours postdose on Day 1, for lunch and dinner, subjects will receive a standardized moderate fat meal. Subjects will be allowed snacks starting after lunch.

ⁿ To be sampled predose on Week 1 only.

Whenever possible, the same individual should complete/rate consistently the following scales and questionnaires as appropriate: ADHD-RS-5 Child, Home Version; Clinical Global Impressions - Severity of Illness; Post Sleep Questionnaire; and Children's Sleep Habits Questionnaire.

Table 2: Schedule of Assessments for Sparse Pharmacokinetic Sampling Portion

Assessment Day	Screening and Washout		Week 1 to 3		Week 4		Follow-up ^a
	D -32 to D -8	D -7 to D -1 Washout	D 1	D 2-7	D 1	D 2-7	

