On Day 7 of Week 4, subset of subjects in the rich PK sampling portion will be required to remain at the CRC through 8 hours postdose. Following completion of the 8-hour PK sample collection, per investigator's discretion, subjects will have the option to remain at or leave the CRC. If they leave the CRC, subjects will either return to the CRC on Days 7, 8, and 9 of Week 4 for the 12-hour, 16-hour, 24-hour, and 48-hour postdose blood sample collections or, if the option is available at their clinical site, a qualified person may visit the subject for the 12-hour, 16-hour, and 24-hour postdose blood sample collections, but they must return to the clinic for the 48-hour blood sample collection.

Sparse PK Sample Scheme (4 Samples/Subject) Collection

Predose PK samples will be collected on Day 1 of Weeks 1 to 3 and on Day 8 of Week 4 (24 hours after dosing on Day 7 of Week 4) for subjects in the sparse PK sampling subset.

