4.4 Discontinuation of Subjects

A subject may withdraw from the study, or the parent/LAR may withdraw the subject from the study, at any time for any reason without prejudice to their future medical care by the physician or at the institution. The investigator or sponsor may withdraw the subject at any time (eg, in the interest of subject safety). The investigator is encouraged to discuss withdrawal of a subject from investigational product with the medical monitor when possible.

If investigational product is discontinued, regardless of the reason, the early withdrawal evaluations listed in [Table 1](#) and [Table 2](#) are to be performed as completely as possible. Whenever possible, all discontinued subjects should also undergo the protocol-specified follow-up. Comments (spontaneous or elicited) or complaints made by the subject must be recorded in the source documents. The reason for termination, date of stopping investigational product, and the total amount of investigational product taken must also be recorded in the source document.

Subjects who discontinue may be replaced at the discretion of the investigator and sponsor to ensure at least 10 completers in each of the PK sampling portions of the study (of which at least 2 subjects in the rich PK sample subset and at least 3 subjects in the rich PK sample subset should be female).

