9.6 Study Population

The **screened set** will consist of all subjects who have provided consent.

The **enrolled set** will consist of all subjects who have been assigned a subject identification number.

The **safety set** will consist of all enrolled subjects who have taken at least 1 dose of investigational product.

The **PK set** will consist of all subjects in the safety set for whom at least 1 postdose PK blood sample was collected.

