#### 12.1.1 Concentration Data

During this study blood samples for the determination of plasma *d*- and *l*-amphetamine concentrations will be drawn from each subject. For subjects enrolled onto the Rich PK sample portion blood samples will be collected on Day 1 of Week 1 at predose, and on Day 7 of Week 4 at predose, and at 2, 5, 8, 12, 16, 24, and 48 hours after administration of the investigational product. For subjects enrolled onto the Sparse PK sample portion blood samples will be collected on Day 1 of Weeks 1 to 3, and on Day 8 of Week 4 at predose only. Plasma *d*- and *l*-amphetamine concentrations will be measured using the most current validated bioanalytical method.

Individual plasma *d*- and *l*-amphetamine concentrations will be listed by subject, week, day, and time based on the PK set and summarized by time based on the PK set with the following descriptive statistics: n, arithmetic mean, SD, coefficient of variation (CV%), median, minimum, maximum, and geometric mean. The individual and mean plasma *d*- and *l*-amphetamine concentration versus time profiles will be presented in figures on both linear and semi-logarithmic concentration scales for the Rich PK sampling portion. Mean ( $\pm$ SD) plasma *d*- and *l*-amphetamine concentration versus time profiles will be presented using nominal time and individual plasma *d*- and *l*-amphetamine concentration versus time profiles will be presented using actual time based on the PK set. Individual and mean ( $\pm$ SD) plasma *d*- and *l*-amphetamine trough concentrations versus day will be presented in figures on linear concentration scale.

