## 17. CHANGES TO ANALYSES SPECIFIED IN PROTOCOL

The PK parameters  $AUC_{0-\infty}$  and  $V_z/F$  for *d*- and *l*-amphetamine have been omitted from the PK analysis, given that only steady-state PK concentrations will be available. These parameters are not appropriate for calculation and interpretation in multiple dosing scenarios. There are no other changes from the PK analysis methods stated in the protocol.

Protocol section 9.8 (Safety Analyses) states: Treatment-emergent AEs are defined as AEs that started or deteriorated on or after the date of the first dose of investigational product, and no later than 3 days following the **first** dose of investigational product. Since this is a multiple-dose study and the dose will be administered daily as a single dose for 28 days, the definition of TEAE in the protocol will exclude the AEs started or deteriorated on or after the fourth dose, which will not be appropriate for safety analysis. The following definition for TEAEs is used in the Statistical Analysis Plan: Treatment-emergent AEs are defined as AEs that started or deteriorated on or after the date of the first dose of investigational product, and no later than 3 days following the **last** dose of investigational product.

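### Two minor SAP wording points: the PK set omits the protocol's postdose condition without declaring it, and counting BLQ as zero leaves the geometric mean 0 or undefined at time points with mixed results

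*SAP*

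**What the plan says.** **PK set.** Protocol 9.6, with the same condition in the synopsis, defines the set as "all subjects in the safety set for whom at least 1 postdose PK blood sample was collected". SAP 4.4 reads: "The PK set will consist of all subjects in the safety set for whom at least 1 PK blood sample was collected". SAP 17 declares two changes: the omission of AUC0-∞ and Vz/F, and a corrected TEAE window. On pharmacokinetics it then says: "There are no other changes from the PK analysis methods stated in the protocol". The PK set is not mentioned there.

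**Sampling.** Each subset has one sample before any drug is taken. For the rich subset, footnote n to Protocol Table 1 says of the Day 1 sample: "To be sampled predose on Week 1 only". For the sparse subset, SAP 12.1.1 schedules samples "on Day 1 of Weeks 1 to 3, and on Day 8 of Week 4 at predose only".

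**BLQ values.** SAP 12.1.2 counts a BLQ concentration as zero in the summary statistics at each time point. Its one exception is the case where all values are BLQ; the mean is then shown as zero and no other statistics are given. SAP 12.1.1 lists eight statistics for concentrations by time, and the geometric mean is one of them.

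**The concern.** A PK set is meant to identify the children who have information about the drug in plasma. A sample taken before the first dose carries none. Every child is scheduled to give such a sample, so under the SAP wording the PK set comes close to being the safety set. A difference from the protocol in an analysis set should also be visible in the section that exists to declare changes. PK is part of the primary objective and only about 24 children are planned, so membership should be settled before database lock.

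The BLQ point is independent of this. A geometric mean cannot be combined with zeros. Where some but not all values are BLQ, the SAP asks for a statistic that its own rule makes meaningless. Two programmers could then resolve the conflict differently and report different numbers from the same data.

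**Working it through.** The plan states no figure on either point, so the check compares texts and adds short arithmetic.

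**1. Who is in which set**

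| Child | SAP 4.4 | Protocol 9.6 |
|---|---|---|
| Not dosed | out | out |
| Dosed, no PK sample | out | out |
| Dosed, Week 1 predose sample only | **in** | **out** |
| Dosed, rich subset, sampled after the Week 4 Day 7 dose | in | in |
| Dosed, sparse subset, on-drug troughs | in | in if *postdose* means after the first dose; out if it is read from the sample label |

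The last row shows a weakness in the protocol's term. All four sparse samples are called predose, but three of the four follow the first dose. The last is taken "on Day 8 of Week 4 (24 hours after dosing on Day 7 of Week 4", which Protocol 7.1.2 places about 24 hours after the final dose, so no dose comes after it.

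**2. Time to the next scheduled PK sample**

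- Rich: Week 4 Day 7 is study day 3 × 7 + 7 = 28, and 28 − 1 = 27 days after the first dose.
- Sparse: Week 2 Day 1 is study day 7 + 1 = 8, and 8 − 1 = 7 days after the first dose.

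These are schedule gaps for children who stay in the study. They show that a window exists, not how many children fall into it.

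**3. Size of the PK-set difference**

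Let k be the number of dosed children with only the Week 1 predose sample, out of about 24 (SAP 2.5). The SAP set has 24 and the protocol set 24 − k.

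- k = 0: 24 against 24.
- k = 1: 1/24 = 4.2%.
- k = 4, that is, all of 24 enrolled minus 20 completers (illustration only): 4/24 = 16.7%.

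The last value is not an upper bound, because Protocol 4.4 provides: "Subjects who discontinue may be replaced at the discretion of the investigator and sponsor to ensure at least 10 completers". The documents give no value for k.

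**4. Outputs that would carry the extra child**

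- The PK-set count (SAP 5).
- Tables 14.1.4.1.2 and 14.1.4.2.2 (demographic and baseline characteristics, PK set).
- Listings 16.2.1.3 (set classification), 16.2.5.3 and 16.2.5.4 (concentrations).
- The Week 1 predose row of Tables 14.2.5.1 and 14.2.5.2.
- Trough Figures 14.2.5.3 and 14.2.5.6, if they include that sample.

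SAP 12.1.3 derives the noncompartmental parameters from rich-subset profiles only. A child with no sample after dosing yields none, so AUC, Cmax and CL/F do not change.

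**5. Geometric mean with BLQ set to zero**

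GM = (x₁ × … × xₙ)^(1/n) = exp[mean(ln x)]. One zero makes the product zero, and ln(0) is undefined. The concentrations below are assumed, because the documents give neither an LLOQ nor expected values.

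- Nine values of 10 and one BLQ: arithmetic mean 90/10 = 9.0; median 10; GM = 0, or undefined on the log scale.
- Three BLQ plus 5, 6, 7, 8, 9, 10, 11: GM = 0 under the SAP rule. It is 7.74 over the 7 quantifiable values, and 2.76 if each BLQ is replaced by an assumed 0.25.

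If software silently drops ln(0), the second example gives 7.74 on n = 7, which no longer follows the stated rule. SAP 12.1.2 covers the all-BLQ case and not the mixed one.

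**The case against.** Several counterarguments have force.

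- **SAP 17 may not be wrong.** The quoted sentence speaks of analysis methods, while the PK set is defined under Study Population in Protocol 9.6, apart from the PK analyses in 9.7. A reader might infer that the sentence is false; the text does not clearly support that. What stands is the omission. Protocol 9.7.1 and SAP 12.1 base all PK analyses on this set, and SAP 17 explains a one-word change to the TEAE definition in full. SAP 1 also cites protocol administrative change #1 (31 Oct 2017), which was not available here.
- **The protocol wording is not simply the better one.** Read by sample label, it could exclude the sparse subset. Restoring the word alone would not settle membership.
- **Withdrawn children may be sampled.** Protocol 4.4 says the early withdrawal evaluations "are to be performed as completely as possible". A child sampled at withdrawal after dosing has a sample after the first dose. In the copy reviewed, the PK rows of Tables 1 and 2 lack the withdrawal footnote that the adverse-event and concomitant-medication rows carry. The table layout in that copy is imperfect, so this stays open.
- **The BLQ problem may never arise.** Counting planned geometric means gives 9 rich + 4 sparse = 13 time points × 2 analytes = 26. With Week 1 predose and 24 hours pooled across subsets it is 11 × 2 = 22. A reader might take 22 to 26 as the number at risk. It is only the number governed by the rule. Week 1 predose follows a 7-day exclusion of ADHD medication and may be entirely BLQ, which the SAP handles. For on-drug times nothing in the documents shows that any value would be BLQ. A convention may also exist in the separate table specifications.

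**Conclusion.** Both points hold on the text, and both are minor.

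1. SAP 4.4 admits a dosed child whose only PK sample precedes the first dose, the protocol does not, and SAP 17 is silent. Each such child is 4.2% of a planned 24, and the number may be 0. This rests on the protocol as supplied, without administrative change #1.
2. The SAP's BLQ rule makes the geometric mean 0 or undefined at any time point with some but not all values BLQ. It touches one of eight concentration statistics. How many time points are affected is unknown and may be 0.

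A reader might infer that the exposure estimates are biased. The documents do not support that: AUC, Cmax and CL/F come only from rich-subset profiles, and the PK analysis is descriptive. Nor is the 16.7% illustration an expected effect; it assumes that four children all leave with no later sample.

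**What to change.** - **SAP 4.4:** define the PK set as safety-set subjects with at least 1 PK sample collected after the first dose of investigational product. This keeps the sparse on-drug troughs whatever their label and leaves out children with only a pre-drug sample.
- **SAP 17:** declare this wording as a clarification of Protocol 9.6. No protocol change is then needed; aligning Protocol 9.6 as well would be one.
- **SAP 12.1.2:** exempt the geometric mean from the zero rule. At time points with any BLQ value, either do not report it or compute it over the quantifiable values with that n shown. Either convention is acceptable if fixed in advance. In both cases give the number BLQ with the median and range.

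The cost is a few sentences in the SAP before database lock. The PK set may be slightly smaller, and some geometric means may go unreported or rest on a reduced n. No study procedure changes.
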